#### 4.5.5.11.1. Acute Renal Events

Acute renal events associated with chronic renal failure exacerbation will be captured.

Severe/serious renal events from the SMO search below will be considered AESIs.

The counts and percentages of participants with acute renal events will be summarized by treatment by using the MedDRA PTs contained in any of the following SMQs:

#### • Acute renal failure:

o Narrow terms in Acute renal failure SMQ (20000003)

#### • Chronic kidney disease:

o Narrow terms in Chronic kidney disease SMQ (20000213)

In addition, a listing of participants with treatment-emergent acute renal events may be provided, if deemed necessary.

#### 4.5.5.11.2. Dehydration

Dehydration events will be captured in the following SMQ and summarized. Severe/serious dehydration events will be considered as AESI:

• Narrow terms in Dehydration SMQ (20000232)

The counts and percentages of participants with dehydration will be summarized by treatment and PT and ordered by decreasing frequency. A listing of participants with treatment-emergent dehydration events may be provided, if deemed necessary.

# 4.5.5.12. Thyroid Safety Monitoring

#### 4.5.5.12.1. Calcitonin

Observed calcitonin data (a thyroid-specific laboratory assessment) will be summarized by treatment and nominal visit.

The counts and percentages of participants with a maximum postbaseline calcitonin value in the following thresholds will be provided by treatment and baseline calcitonin value: ( $\leq$ 20 ng/L,  $\geq$ 20 ng/L to  $\leq$ 35 ng/L,  $\geq$ 35 ng/L). Postbaseline:  $\leq$ 20 ng/L,  $\geq$ 20 ng/L to  $\leq$ 35 ng/L,  $\geq$ 35 ng/L to  $\leq$ 50 ng/L,  $\geq$ 50 ng/L to  $\leq$ 100 ng/L, and  $\geq$ 100 ng/L.

# 4.5.5.12.2. C-Cell Hyperplasia and Thyroid Malignancies

Treatment-emergent thyroid malignancies and C-cell hyperplasia will be considered as AESI. Detailed searching criteria can be found in Appendix 6 (Section 6.6).

The counts and percentages of participants with treatment-emergent thyroid C-cell hyperplasia and malignancies will be summarized by treatment and PT ordered with decreasing frequency. In addition, a listing of participants with treatment-emergent thyroid C-cell hyperplasia and neoplasms may be provided if deemed necessary.

# 4.5.5.13. Treatment-Emergent Arrhythmias and Cardiac Conduction Disorders

Severe/serious treatment-emergent arrhythmias and cardiac conduction disorders will be considered as AESI.

The treatment-emergent arrhythmias and cardiac conduction disorders events will be identified using the MedDRA PTs. Detailed searching criteria can be found in Appendix 6 (Section 6.6).

The counts and percentages of participants with treatment emergent arrhythmias and cardiac conduction disorders will be summarized by treatment and PT nested within SMQ. The PT will be ordered with decreasing frequency within SMQ. A listing of participants with treatment-emergent arrhythmias and cardiac conduction disorders may be provided if deemed necessary.

#### 4.5.5.14. Treatment of Overdose

A listing of patients reporting AEs related to overdosing of tirzepatide may be provided.

# 4.5.5.15. Abuse Potential

To identify AE terms suggestive of abuse liability potential, narrow terms from the SMQ Drug abuse and dependence (20000101) will be used. The counts and percentages of participants will be summarized by treatment group with decreasing frequency.

# 4.6. Other Analyses

#### 4.6.1. Health Outcomes

The patient-reported outcome questionnaires will be analyzed using the mITT population on the EAS, unless specified otherwise.

Item-level missingness is dealt with as per the instrument developers' instruction.

Additional psychometric analyses will be performed by the Value Evidence Outcomes group at Lilly and documented in a separate analysis plan.

# 4.6.1.1. Short-Form-36 Health Survey Version 2, Acute Form

Per copyright owner, the QualityMetric Health Outcomes™ Scoring Software (PRO\_CoRe V2.0) will be used to derive the following domain and component scores:

- Mental Component Summary (MCS)
- Physical Component Summary (PCS)
- Physical Functioning domain (PF)
- Role-Physical domain (RP)
- Bodily Pain domain (BP)
- General Health domain (GH)
- Vitality domain (VT)
- Social Functioning domain (SF)
- Role-Emotional domain (RE), and
- Mental Health domain (MH).

For each above domain and component summary scores parameter, the raw scores will be transformed into the domain scores (t-scores) and the following analyses for the actual value and change from baseline value will be conducted:

- descriptive summaries by treatment group, and
- analysis described in Table GPHZ.4.11.

If data allowed, analysis for SF-36 physical function domain score analysis described in Table GPHZ.4.11 will be conducted to evaluate the treatment effect in participants who have limitations in physical function at baseline, which is defined as PGIS response at baseline of "moderately limited," "very much limited," or "extremely limited."

#### 4.6.1.2. Impact of Weight on Quality of Life-Lite Clinical Trials

The following parameters will be included from IWQOL-Lite-CT:

• IWQOL Lite CT total score (all items: items 1 through 20)

- Physical Function composite score (5 items: items 1 through 3, 16, 17)
- Physical composite score (7 items: item 1 through 5, 16, 17), and
- Psychosocial composite score (13 items: item 6 through 15, 18, 19, 20).

IWQOL-Lite-CT total and composite scores range from 0 to 100, with higher scores reflecting better levels of functioning.

IWQOL-Lite-CT scores are computed according to the IWQOL-Lite scoring rules (Kolotkin et al. 2002) as following:

- Each composite raw score will be calculated if a minimum of 50% of the items for that composite has a non-missing value; the total score will be calculated if a minimum of 75% of all 20 items has a non-missing value.
  - o physical composite score: 4 of 7 items
  - o physical function composite score: 3 of 5 items
  - o psychosocial composite score: 7 of 13 items
  - o IWQOL-Lite-CT total score: 15 of 20 items
- If the minimum required number of items is answered then:
  - The average of the valid non-missing responses corresponding to the items in the total or each composite will be calculated (1 = "never" or "not at all true" and 5 = "always" or "completely true").
  - The composite score will be then calculated by transforming the raw composite score to the 0 (worst)-to-100 (best) metric using the following formula for every patient at each time point:

$$100 (S_{max} - C_{avg})/(S_{max} - S_{min})$$

- $C_{avg}$  is the raw average score of all non-missing item responses in the composite; this average must be a number between 1 and 5, inclusive
- $S_{max}$  is the maximum possible raw score value (i.e., 5)
- $S_{min}$  is the minimum possible raw score value (i.e., 1)
- Inserting the maximum and minimum possible score values, the formula is reduced to  $100 (5 C_{avg})/4$ .

For total and each composite score, the following analyses for the actual value and change from baseline value will be conducted:

- descriptive summaries by treatment group and
- ANCOVA analysis described in Table GPHZ.4.11.

#### 4.6.1.3. EQ-5D-5L

Generic health-related quality of life will be assessed using the EuroQol – 5 Dimension – 5 Level (EQ-5D-5L) (EuroQoL Group 2015). The EQ-5D-5L is a standardized 5-item instrument for use as a measure of health outcome. It provides a simple descriptive profile and a single index value for health status that can be used in the clinical and economic evaluation of health care as well as population health surveys. The EQ-5D-5L comprises 5 dimensions of health (mobility, self-care, usual activities, pain/discomfort, and anxiety/depression). The 5L version, introduced in 2005, scores each dimension at 5 levels (no problems, slight problems, moderate problems, severe problems, unable to perform/extreme problems), for a total of 3125 possible health states. In addition to the health profile, a single health state index value can be derived based on a formula that attaches weights to each of the levels in each dimension. This index value ranges between <0 (where 0 is a health state equivalent to death; negative values are valued as worse than dead) to 1 (perfect health) (Dolan 1997). In addition, the EQ visual analog scale (VAS) records the respondent's self-rated health status on a vertical graduated (0 to 100) scale. In conjunction with the health state data, it provides a composite picture of the respondent's health status. The EQ-5D-5L is used worldwide and is available in more than 170 different languages. Details on the instrument, and scoring, organizing, and presenting the data collected will follow C2H guidelines (Ikeda et al. 2015; C2H 2019).

# 4.6.1.4. Patient Global Impression of Status for Physical Activity

Study participants will be asked to complete a PGIS item. This is a patient-rated assessment of current health limitation and is rated on a 5-point scale ranging from "1- not at all limited" to "5- extremely limited."

The counts and percentages of participants for Patient Global Impression of Status for Physical Activity (PGIS) response categories at each time point will be summarized by nominal visit and by treatment. A shift table from baseline to postbaseline of 5 PGIS response categories at each postbaseline visit by treatment will be created.

# 4.6.1.5. Health Outcome Analysis

**Table GPHZ.4.11. Health Outcome Measures** 

Analysis variable	Criteria/Measures	Analysis set	Analysis method	Additional Information
Change in patient-reported physical functioning (72 weeks)	Mean change from BL in SF 36v2 acute form physical functioning domain score	Efficacy analysis set	ANCOVA model in Section 4.4.2.1	
	Mean change from BL in IWQOL-Lite- CT Physical Function score	Efficacy analysis set	ANCOVA model in Section 4.4.2.1	
Change in patient-reported health status (72 weeks)	Mean change from BL in EQ-5D-5L score  Index score VAS score	Efficacy analysis set	ANCOVA model in Section 4.4.2.1	
Change in SF-36v2 acute scores other than physical functioning (72 weeks)	Mean change from BL in  role-physical score bodily pain score general health score vitality score social functioning score role-emotional score mental health score physical component summary mental component summary	Efficacy analysis set	ANCOVA model in Section 4.4.2.1	Exploratory objective
Change in IWQOL-Lite-CT scores other than physical functioning (72 weeks)	Mean change from BL in  physical score  psychosocial score  total score	Efficacy analysis set	ANCOVA model in Section 4.4.2.1	Exploratory objective
Change in Patient Global Impression of Status (72 weeks)	Shift of the ordinal response category from BL	Efficacy analysis set	Shift table described in Section 4.6.1.4	Exploratory objective

Abbreviations: ANCOVA = analysis of covariance; BL = baseline; EQ-5D-5L = EuroQol - 5 Dimension - 5 Level; IWQOL-Lite-CT = Impact of Weight on Quality of Life-Lite-Clinical Trials Version; SF-36v2 = Short Form 36-item Health Survey Version 2; VAS = Visual Analog Scale.

# 4.6.2. Dietary Evaluation

All patients who additionally agree to participate in taking dietary evaluation will be in the analysis population for dietary evaluation (meal intake and appetite sensation) analyses. Dietary evaluation analyses will be guided by the efficacy estimand in EAS.

#### **4.6.2.1. Meal Intake**

Meal record will be collected before each meal (including breakfast, lunch, dinner, and snacks) for a day. In case if patients cannot finish them all, meal records after the meal will be collected. Meal records will be collected on 3 consecutive or non-consecutive days during the week (at least 1 day should be working day and at least 1 day should be resting day) immediately before the visits: Visit 3 (Week 0), Visit 9 (Week 24), Visit 16 (Week 52), and Visit 21 (Week 72). The Lilly-designated vendor will calculate the volume of total fats (g), total carbohydrates (g), total protein (g), and total caloric intake (kcal) based on the meal record.

For each participant and scheduled visit, daily parameters (sum of all days for each parameter at breakfast, lunch, dinner, and snack divided by the number of days) will be derived for following:

- Total caloric intake per day (kcal)
- Total fats per day (g)
- Total carbohydrates per day (g)
- Total protein per day (g)

For each participant and scheduled visit, daily caloric intake will be derived for following:

- Total fats per day (kcal) =  $9 \text{ (kcal/g)} \times \text{ total fats per day (g)}$
- Total carbohydrates per day (kcal) = 4 (kcal/g) × total carbohydrates per day (g)
- Total protein per day (kcal) =  $4 \text{ (kcal/g)} \times \text{ total protein per day (g)}$

For each participant and scheduled visit, percent of each component will be derived for following:

- Percent of fats per day (%) =  $100 \times \text{total fats per day (kcal)} / \text{total caloric intake per day (kcal)}$
- Percent of carbohydrates per day (%) =  $100 \times \text{total}$  carbohydrates per day (kcal) / total caloric intake per day
- Percent of protein per day (%) =  $100 \times \text{total protein per day (kcal)} / \text{total caloric intake}$  per day

For each participant and scheduled visit, snack caloric intake per day will be derived by:

• Sum of all days for caloric intake at snack / number of days

Analysis method is described in the Section 4.6.2.3.

# 4.6.2.2. Appetite Sensation

The subjective rating of appetite sensations is measured by a 100-mm VAS for parameters of hunger, fullness, satiety, and prospective food consumption including snacks. The meal record will be collected on 3 consecutive or non-consecutive days during the week (at least 1 day should be working day and at least 1 day should be resting day) immediately before the visits: Visit 3 (Week 0), Visit 9 (Week 24), Visit 16 (Week 52), and Visit 21 (Week 72). For each meal, including breakfast, lunch, dinner and snacks, participant should complete the VAS 10 minutes before the meal and immediately after the meal. The timing of the record should be on the same date as the meal intake record. In case of frequent snacking on each recording day, if a participant consumes several snacks a day, they will be asked to complete the meal intake record for all snacks, but will only be required to complete VAS measurement for the first afternoon snack. The VAS is a validated tool to assess appetite sensation parameters (Flint et al. 2000). The VAS is presented as a 10-cm (100-mm) line, anchored by verbal descriptors, usually "extremely" and "not at all." Participants are required to rate their subjective sensations on four 100-mm scales combined with the questions:

- "How hungry do you feel right now?"
- "How satisfied do you feel right now?"
- "How full do you feel right now?"
- "How much food do you think you could eat right now?"

A staff member will use a caliper to measure the distance from 0 to the mark that the participant placed on the VAS and record the measurement in the source document.

Overall appetite score is calculated as the average of the 4 individual scores (van Can et al. 2014) below:

{[Satiety] + [Fullness] + (100 – [Prospective food consumption]) + (100 – [Hunger])} / 4.

The higher overall appetite score indicates less appetite, and the lower score indicates more appetite.

Analysis method is described in the Section 4.6.2.3.

# 4.6.2.3. Dietary Evaluation Analysis

**Table GPHZ.4.12. Dietary Evaluation Measures** 

Analysis variable	Criteria/Measures	Analysis set	Analysis method	Additional Information
Change in dietary evaluation based on the meal record (24, 52, and 72 weeks)	Mean change from BL in  Total fats (g) Total carbohydrates (g) Total proteins (g) Total caloric intake (kcal) Total fats (kcal) Total carbohydrates (kcal) Total proteins (kcal) Total fats (%) Total fats (%) Total carbohydrates (%) Total proteins (%) Snack caloric intake (kcal)	Efficacy analysis set – agreed dietary evaluation	MMRM model in Section 4.3.2.1	
Change in dietary evaluation based on appetite sensation (24, 52, and 72 weeks)	Mean change from BL in  Satiety Fullness Prospective food consumption Hunger Overall appetite score	Efficacy analysis set – agreed dietary evaluation	MMRM model in Section 4.3.2.1	

Abbreviations: BL = baseline; MMRM = mixed model for repeated measures.

# 4.6.3. Subgroup analyses

# 4.6.3.1. Subgroup Analysis of Efficacy Endpoints

Efficacy subgroup analyses will be guided by the efficacy estimand in EAS. Subgroup analyses by the following baseline characteristics will be provided:

- age ( $<65, \ge 65 \text{ years}$ )
- sex (female and male)
- baseline BMI (<35,  $\ge35$  kg/m^2)
- baseline BMI ( $\ge 27$  and < 30,  $\ge 30$  and < 35,  $\ge 35$  and < 40,  $\ge 40$  kg/ m^2)
- glycemic status at screening (normoglycemia versus IGT)
- hyperlipidemia status at screening (TG;  $\geq$ 150 and <150 mg/dL)
- NAFLD status at screening (HFF; ≥5% and <5%), analysis population will be the mITT excluding subjects with missing HFF measure at screening

For the reporting in the CSR, the outcome measures for the subgroup analyses will include:

- Percent change in body weight from randomization at 72 weeks.
- Proportion of participants achieving at least 5% body weight reduction from randomization to 72 weeks.

For the other purpose (eg. the publication), the outcome measures for the subgroup analyses will include:

- Proportion of participants achieving at least 10%, 15% and 20% body weight reduction from randomization to 72 weeks.
- Change in waist circumference (cm) from randomization to 72 weeks.
- Change in VAT area (cm^2), SAT area (cm^2) and VAT/SAT ratio from randomization to 72 weeks.
- Change in HFF (%) from randomization to 72 weeks.
- Change in Short-Form-36 Health Survey version 2 from randomization to 72 weeks.
- Change in IWQOL-Lite-CT Physical Function score from randomization to 72 weeks.

For the percentage change in body weight from randomization at 72 weeks, for each subgroup analyses aforementioned, the following analyses will be conducted:

• Conduct MMRM model on the subgroup only with terms of treatment group, visit, treatment-by-visit-interaction and stratification factors as fixed effects, and baseline body weight as a covariate. Variance-covariance structure for within-patient errors will be same as Section 4.3.2.1.

• Full MMRM model: treatment group, visit, subgroup, treatment-by-visit-interaction, treatment-by-subgroup-interaction, subgroup-by-visit-interaction, treatment-visit-subgroup-interaction, and stratification factors as fixed effects, and baseline body weight as a covariate. Variance-covariance structure for within-patient errors will be same as Section 4.3.2.1.

For the percentage of participants achieving at least 5% body weight reduction at 72 weeks, for each subgroup analyses aforementioned, the following analyses will be conducted:

- Conduct logistic regression model on the subgroup only with terms of treatment group, and stratification factors as fixed effects, and baseline body weight as a covariate. Variance-covariance structure for within-patient errors will be same as Section 4.3.2.2.
- Full logistic regression model: treatment group, subgroup, treatment-by-subgroup-interaction, and stratification factors as fixed effects, and baseline body weight as a covariate. Variance-covariance structure for within-patient errors will be same as Section 4.3.2.2.

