Self-harm supplement form	X	X	X	At Visit 2, self-harm supplement form can be performed on same day as OGTT test.
Self-harm follow-up form	X	X	X	At Visit 2, self-harm follow up form can be performed on same day as OGTT test.
CT and MRI				
Visceral and subcutaneous adipose tissue imaging		X		Image analysis to be conducted centrally. Either CT or MRI can be used for the adipose tissue imaging. The chosen method needs to be consistent across all visits for each participant.

Activity	Scre	ening	Randomization	Comments
Visit number	1	2	3	
Week of treatment	-4	-2	0	
Allowable deviation (days)	NA	-7/+3	-3/+7	The visit date after randomization visit is determined in relation to the date of the randomization visit (\pm the allowed visit window).
Fasting visit	X	X	X	If the participant is not fasting, the participant should be called in for a new visit within the visit window. Patients must be fasting at least 10 hours before blood sampling.
Hepatic fat fraction by MRI-PDFF (only for participants who enroll as NAFLD)		X		Image analysis to be conducted centrally. For individuals where the MRI-PDFF image quality is in question, and re-capturing and assessment of the MRI image is required before 1 st dose of study drug, due to the turnaround time of a central image analysis, a flexible screening window will be allowed. In such scenarios, a Visit 3 that occurs outside of the visit window will not be considered a protocol deviation.
2-Hour OGTT				
Glucose, insulin, and c-peptide		X		2-Hour OGTT test can occur 0 to 4 days prior to the visit.
Physical evaluation				
Physical examination	X			
Height	X			
Weight	X		X	Body weight must be measured in fasting state.
Waist circumference			X	
Electrocardiogram			X	Triplicate ECGs should be collected centrally at Visit 3.
Vital signs (sitting BP and PR)	X		X	Vital sign measurements should be taken before collection of blood samples for laboratory testing, at visits where required. The participant should sit quietly for 5 minutes before vital sign measurements are taken. For each parameter, 2 measurements will be taken using the same arm; the recordings should be taken at least 1 minute apart.
Clinical laboratory tests				
Hematology	X			
Clinical chemistry panel	X		X	
Other chemistry				

Activity	Scre	ening	Randomization	Comments
Visit number	1	2	3	
Week of treatment	-4	-2	0	

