5.1. Inclusion Criteria

Participants are eligible to be included in the study only if all of the following criteria apply:

Age

1. Participant must be 20 years or older at the time of signing the informed consent.

Type of Participant and Disease Characteristics

- 2. Have BMI of
 - \geq 27 kg/m² and <35 kg/m² with at least 2 obesity-related health problems or
 - \cdot \geq 35 kg/m² with at least 1 obesity-related health problems
 - Health problems are IGT, hyperlipidemia, or NAFLD at screening (Visit 1 and Visit 2).
 - a. IGT: have oral glucose tolerance test (OGTT) 0-hour glucose of ≥110 mg/dL and/or OGTT 2-hour glucose of ≥140 mg/dL at Visit 2 and do not meet diagnostic criteria for diabetes mellitus (DM) at Visit 1 and Visit 2. In this study, IGT is defined to include impaired fasting glucose also described as "Borderline type" according to Japanese Clinical Practice Guideline for Diabetes 2019 (Araki et al. 2020).
 - b. hyperlipidemia: have fasting triglyceride ≥150 mg/dL at screening at Visit 1 and 2
 - c. NAFLD (participants with NAFLD can be enrolled ONLY at clinical sites which have magnetic resonance imaging [MRI] proton density fat fraction [PDFF] availability and/or can obtain support from imaging sites for MRI-PDFF)
 - i. have hepatic fat fraction (HFF) ≥5% as measured by MRI-PDFF imaging (central evaluation) at Visit 2
- 3. Have a history of at least 1 self-reported unsuccessful dietary effort to lose body weight
 - a. In the investigator's opinion, are well-motivated, capable, and willing to learn how to self-inject study intervention, as required for this protocol (visually impaired persons who are not able to perform the injections must have the assistance of a sighted individual trained to inject study intervention; persons with physical limitations who are not able to perform the injections must have the assistance of an individual trained to inject study intervention) and
 - inject study intervention (or receive an injection from a trained individual if visually impaired or with physical limitations)
 and
 - c. follow study procedures for the duration of the study, including, but not limited to: follow lifestyle advice (for example, dietary restrictions and exercise plan), maintain a study diary, and complete required questionnaires

Sex

4. Male and/or female

Contraceptive use by men or women should be consistent with local regulations regarding the methods of contraception for those participating in clinical studies.

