6.3. Measures to Minimize Bias: Randomization and Blinding

Interactive web-response system

All participants will be randomly assigned to study intervention using a central interactive-web response system (IWRS) at the end of Visit 3 after participant's eligibility is confirmed. Before the study is initiated, the log in information and directions for the IWRS will be provided to each site. Study intervention will be dispensed at the study visits summarized in the Schedule of Activities (Section 1.3).

The randomization will be stratified by

- baseline IGT (yes or no)
- baseline hyperlipidemia (yes or no)
- baseline NAFLD (yes or no), and
- sex

Blind break

Investigators, site staff, clinical monitors and participants will remain blinded to the treatment assignments until the study is complete.

The IWRS will be programmed with blind-breaking instructions. In case of an emergency, the investigator has the sole responsibility for determining if unblinding a participant's intervention assignment is warranted. Participant safety must always be the first consideration in making such a determination. If a participant's intervention assignment is unblinded, the sponsor must be notified immediately after breaking the blind. The date and reason that the blind was broken must be recorded in the source documentation.

If an investigator, site personnel performing assessments, or participant is unblinded, the participant must be discontinued from the study. In cases where there are ethical reasons to have the participant remain in the study, the investigator must obtain specific approval from a Lilly clinical research physician (CRP) and/or clinical research scientist (CRS) for the participant to continue in the study.

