9.4.7. Other Analyses

9.4.7.1. Subgroup Analyses for Primary Outcome

Details of the subgroup analyses will be shown in the SAP.

The following subgroup variables will be considered (but not limited to):

- age (<65 years and ≥65 years)
- sex (female and male)
- baseline BMI (≥ 27 and ≤ 30 , ≥ 30 and ≤ 35 , ≥ 35 kg/m²)
- glycemic status at screening (normoglycemia versus IGT)
- hyperlipidemia status at screening (TG; ≥150 and <150 mg/dL)
- NAFLD status at screening (HFF; ≥5% and <5%)

The outcome measures for the subgroup analyses will include

- percent change in body weight from randomization at 72 weeks, and
- percentage of participants achieving at least 5% body weight reduction at 72 weeks.

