- Blood pressure must be taken with a same type of sphygmomanometer (e.g., sphygmomanometer, mercury manometer) throughout the study.
- If blood pressure and pulse measurements are taken separately, pulse should be taken prior to blood pressure.

Note: In the event pulse measurement cannot be taken via an automated blood pressure instrument, the preferred location for measurement of pulse is the radial artery.

Electrocardiogram

- All digital ECGs will be obtained using centrally provided ECG machines and will be electronically transmitted to a designated central ECG laboratory.
- 12-lead ECGs should be obtained after the subject has rested in a supine position for at least 10 minutes.
- Electrocardiograms should be collected at least 30 minutes prior to collection of blood samples for laboratory testing, including PK samples.
- Triplicate ECGs (obtained at Visit 3) should be obtained approximately 1 minute apart, with all 3 tracings to be obtained within approximately 5 minutes. Measurements that deviate substantially from previous readings should be repeated immediately.

2-Hour Oral Glucose Tolerance Test

- Participants should maintain adequate carbohydrate intake for 3 days prior to the scheduled 2-hour OGTT.
- In the 24 hours preceding the test, participants should refrain from drinking any alcohol or performing any extreme physical activity.
- Participants should fast for at least 10 hours before the administration of the test and should not eat until the test is complete.
- Placement of a venous cannula, preferably in an antecubital vein, is recommended to simplify collection of multiple blood samples for glucose, insulin, and C-peptide at time 0, 30, 60, 90, and 120 minutes.
- Immediately after collection of the time 0 sample, a 75-gram glucose dose will be given orally, using a commercial product approved for this use (and in a total volume of not more than 350 mL).
- The participant should consume the glucose load within 5 minutes.
- The participant should remain minimally active for the duration of the test.

Magnetic Resonance Imaging

[figure not shown]
- Participants will undergo 2 liver and abdominal visceral/subcutaneous adipose tissue-directed MRI evaluations. For participant safety, images should also be over-read locally to assure there are no underlying liver pathologies other than NAFLD/NASH.
- In the event of early termination from the study drug or the study,
 - o the second MRI exam may be performed when

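### The NAFLD subgroup excludes participants with no screening HFF, but HFF is scheduled only for those enrolling as NAFLD, so the <5% level is a selected, probably small group and not the randomised non-NAFLD stratum

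*SAP*

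**What the plan says.** Protocol 9.4.7.1 lists the subgroup variable "NAFLD status at screening (HFF; ≥5% and <5"%) with no rule for missing HFF, and leaves subgroup details to the SAP. SAP 4.6.3.1 keeps the two levels and adds the exclusion: "analysis population will be the mITT excluding subjects with missing HFF measure at screening". It prescribes an MMRM within each level and a full model with interactions, and reports percent weight change and the 5% responder endpoint by subgroup in the CSR.

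Who has an HFF value is set elsewhere:

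- Protocol 1.3 lists the scan at Visit 2 and again at Visit 21 under the label "Hepatic fat fraction by MRI-PDFF (only for participants who enroll as NAFLD").
- Protocol 5.1 makes the scan decide the diagnosis: "have hepatic fat fraction (HFF) ≥5% as measured by MRI-PDFF imaging (central evaluation) at Visit 2". It also restricts sites: "participants with NAFLD can be enrolled ONLY at clinical sites which have magnetic resonance imaging".
- Protocol 5.1 gives other routes into the trial: "Health problems are IGT, hyperlipidemia, or NAFLD at screening (Visit 1 and Visit 2").
- Protocol 8.1.2.3 says nobody counts as NAFLD unless MRI defined it.
- Protocol 6.3 nevertheless stratifies everyone by "baseline NAFLD (yes or no), and" sex, IGT and hyperlipidemia.
- Protocol Appendix 11 reads more widely: "Participants will undergo 2 liver and abdominal visceral/subcutaneous adipose tissue-directed MRI evaluations". HFF is part of the acquisition protocol described there.

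**The concern.** The subgroup is meant to show whether the weight effect differs by NAFLD status. Followed as written, a participant who qualifies through IGT and/or hyperlipidemia has no scheduled HFF and is removed. The people left in the <5% level were thought likely enough to have fatty liver to be scanned, at sites with MRI-PDFF access, and then read negative. They do not represent the trial's non-NAFLD participants.

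NAFLD is a stratification factor and an enrichment target (more than 40% of the population, Protocol 4.1), so readers will look at this row. If the level is small, its estimate will be imprecise and a null interaction will say little. A NAFLD yes/no classification already exists for every randomised participant.

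**Working it through.** **The plan's own figure.** SAP 5 assumes 87 per arm, 25% dropout, an 11-point difference, SD 10 and two-sided alpha 0.025. Evaluable per arm: 87 × 0.75 ≈ 65. The two-sample t-test then has power above 99.9%, consistent with the stated figure of more than 90%. No size or power is given for the NAFLD subgroup.

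**How many participants can lack NAFLD.** 261 × 0.40 = 104.4, so more than 40% means at least 105 with NAFLD and at most 261 − 105 = 156 without.

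**Size of the <5% level under the Schedule.** The documents give no count, so both inputs here are assumptions:

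- p, the share of scans reading ≥5%: 0.70 to 0.95.
- q, the share of scan-negative candidates still eligible through the other problems: 0.25 to 0.75.

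Taking every scan-positive candidate as enrolled, n(<5%) = N(NAFLD) × (1 − p)/p × q, capped at 261 − N(NAFLD).

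| N(NAFLD) | Low: p = 0.95, q = 0.25 | High: p = 0.70, q = 0.75 | Non-NAFLD participants left out |
|---|---|---|---|
| 105 | 1.4 | 33.8 | about 122 to 155 of 156 |
| 157 | 2.1 | 50.5 | about 54 to 102 of 104 |
| 209 | 2.8 | 52 (capped) | 0 to about 49 of 52 |

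The last column is 261 − N(NAFLD) − n(<5%). The assumed range is about 1 to 52 people. The hard bounds are 0, if no scan-negative candidate is randomised, and 156, if every non-NAFLD participant is scanned.

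**Precision within the level.** Evaluable per arm m = (n/3) × 0.75, rounded. The 95% half-width for one dose against placebo is t(0.975; 2m − 2) × 10 × √(2/m). Power is for 11 points at two-sided 0.05. The interaction SE is 10 × √(2/m + 2/26), taking the NAFLD level at its floor (105/3 × 0.75 ≈ 26 per arm).

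| People in level | m per arm | Half-width (points) | Power | Interaction SE |
|---|---|---|---|---|
| 15 | 4 | 17.3 | 0.26 | 7.6 |
| 36 | 9 | 10.0 | 0.59 | 5.5 |
| 60 | 15 | 7.5 | 0.83 | 4.6 |
| 156 | 39 | 4.5 | 0.998 | 3.6 |

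For example, with m = 4: 2.447 × 10 × √0.5 = 17.3. With one evaluable participant per arm the contrast cannot be estimated. The last row is the most that could be recovered by using the whole non-NAFLD stratum; the gain shrinks as the NAFLD share rises.

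**Model.** Weight has 11 scheduled post-baseline measurements, so an unstructured covariance has 11 × 12/2 = 66 parameters, fitted inside each level. In addition, SAP 4.4.1.2 takes baseline health problems from measurements. If that also applies to the stratification factor, the NAFLD term is constant within each HFF level and duplicates the subgroup term in the full model.

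**The case against.** The case for the SAP's rule is sound as far as it goes. An unscanned participant has an unknown HFF, and excluding such people avoids labelling them <5%. SAP 4.4.1.2 prefers measurements to IWRS entries, and Protocol 9.4.7.1 specifies the split by HFF. A yes/no subgroup mixes unscanned with scan-negative people, so its tighter interval belongs to a somewhat different comparison. All of this stands, and it is why the HFF split should be kept.

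A reader might infer that the <5% level is nearly empty, that the comparison cannot be made, or that its model cannot be fitted. The documents do not show any of these:

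- Scan-negative candidates must arise, because the Visit 2 scan decides the diagnosis. The OGTT and the second triglyceride test are done at the same visit, so a candidate may be scanned before the other problems are settled.
- Appendix 11 could be read as giving liver MRI to participants generally. Against that, the Schedule allows CT for adipose imaging, and Protocol 8.1.2.4.2 treats those in the HFF analysis as a subset. The passages need reconciling.
- SAP 4.3.2.1, which governs the covariance here, lists six fallback structures if the unstructured model fails. They help convergence but add no information.

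It would also be wrong to say that the subgroup models ignore the NAFLD randomisation factor. It is a fixed effect in them; it just does not define the subgroup. Nor are the excluded participants lost to the trial: they remain in the primary analysis.

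**Conclusion.** The point holds in a limited form. As written, the HFF <5% level is selected, probably small, and unrepresentative of the randomised non-NAFLD participants, of whom there may be up to 156 of 261. How many are left out depends on the NAFLD share enrolled, on scan yield, and on which reading of the Schedule and Appendix 11 applies. The documents fix none of these beyond the 40% floor.

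The precision figures rest on the plan's SD of 10 and 25% dropout, equal allocation within the level, and a simple two-group comparison at Week 72. If the level holds a few dozen people or fewer, the half-width is about as large as the 11-point effect assumed for the whole trial, or larger. This is one subgroup variable with no alpha allocated to it. The primary result, the analysis sets and the safety analyses are unaffected.

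**What to change.** In SAP 4.6.3.1:

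1. Add a NAFLD subgroup by the randomisation factor (yes versus no/not established) in the full mITT, and make it the main NAFLD comparison. Footnote that the second level includes unscanned people, some of whom may have undetected fatty liver, which may dilute the contrast. Protocol 8.1.2.3 supports not counting them as NAFLD.
2. Keep the HFF ≥5% versus <5% split as supplementary and report the number with measured HFF <5% by arm. Set a minimum count per arm in advance; if it is not met, omit the within-level model and the interaction test for <5%.
3. Reconcile the Schedule of Activities with Appendix 11 on who has HFF measured.
4. Omit the NAFLD stratification term from any model in which it duplicates the subgroup variable.

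The cost is a few sentences and one extra display from data already held. The price is the dilution described in the footnote.
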